10.5 Statistical considerations

The primary HRQoL endpoint that is considered relevant for this study is the Global health/QoL status (GHQs) scale of the QLQ-C30 instrument. Other scales will be analyzed on an exploratory basis as secondary HRQoL endpoints, such as fatigue, communication deficit etc. The financial difficulties scale will not be analyzed.

The GHQs scale will be used as primary outcome of interest for this study. A change of 10 points on the 100-point QLQ-C30 scale will be considered as clinically relevant. The standard deviation of this scale is approximately 20 points. With the 2-sided alpha set at 5% and a power of 80% to detect a difference of 10 points (effect size of 0.5), a minimum of 128 patients (64 per treatment arm) is required. For an effect size of 0.75 (difference of 15 points), 56 patients (28 per treatment arm) are required. Therefore, this study is sufficiently powered to detect differences in HRQoL, although the emphasis is on establishing the magnitude and relevance of HRQoL differences rather than comparative tests.

Data will be scored according to the algorithm described in the EORTC scoring manual. All scales and single items are scored on categorical scales and linearly converted to 0-100 scales.

Changes in HRQoL scores per time point will be evaluated by classifying them according to the 10 point change threshold into 3 categories: improved, stable and deteriorated. Patients without a valid HRQoL outcome will be considered as having deteriorated. In case of discrete numbers (N<10), categories may be combined. The subsequent proportions will be compared between treatment arms using a chi-square test in the intent-to-treat population. In order to assess the robustness of the results, the following sensitivity analyses will be performed: a clinical relevant threshold of 5 and 15 points will be used and patients without a valid HRQoL score will be classified according to the reported reason for non-compliance.

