In addition, steroid dose change (sustained reduction and complete reduction) relative to baseline will be summarized. Sustained reduction of steroid dose is defined as 50% or more steroid dose reduction, relative to baseline, for 50% or more of the time on study drug (ABT-414/TMZ/lomustine). Complete reduction is defined as discontinuation of steroid use for $\geq 25\%$ of the time on study drug (ABT-414/TMZ/lomustine).

- The number and percentage of subjects with objective response status (responders; non-responders) and Kaplan-Meier estimates of PFS for subjects who have sustained steroid reduction and for subjects who have complete steroid reduction, respectively.

Quality of Life

Subject self-reported health related quality of life (HRQoL) outcomes are assessed at the baseline, Week 8 MRI visit (while on-treatment), Week 16 MRI visit (while on-treatment), and Month 6 visit (any time during the 6th and 7th month after the date of

randomization regardless of treatment or progression status) by using the QLQ-C30 version 3 (Table 4) and QLQ-BN20 (Table 5).

The main objective of HRQoL assessment is to determine the impact of ABT-414 on overall global health and HRQoL. A secondary objective is to evaluate the effect of the treatment on the remaining symptoms and functioning scales as treatment-related side effects may have a (temporary) negative influence on the health related domains of HRQoL of these subjects. The QLQ (quality of life questionnaire) comprises distinct scales, each of which represents a different aspect of QoL, and the individual questions on the QLQ are called items.

The QLQ-C30 is composed of global health status/QoL scale; five functional scales (physical, role, emotional, cognitive, and social); three symptom scales (fatigue, nausea and vomiting, and pain); and six single items (dyspnea, insomnia, appetite loss, constipation, diarrhea, and financial difficulties).

Table 4. Scoring the QLQ-C30

QLQ-C30	Item (Question) Numbers	Item Range*
Global health status/QoL		
Global health status/QoL	29, 30	6
Functional scales		
Physical functioning	1, 2, 3, 4, 5	3
Role functioning	6, 7	3
Emotional functioning	21, 22, 23, 24	3
Cognitive functioning	20, 25	3
Social functioning	26, 27	3
Symptom scales/Items		
Fatigue	10, 12, 18	3
Nausea and vomiting	14, 15	3
Pain	9, 19	3
Dyspnea	8	3
Insomnia	11	3
Appetite loss	13	3
Constipation	16	3
Diarrhea	17	3
Financial difficulties	28	

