* Item range is the difference between the possible maximum and the minimum responses to individual items; most items take values from 1 to 4, giving range = 3.

Table 5. Scoring the QLQ-BN20

QLQ-BN20	Item (Question) Numbers	Item Range
Symptom scales		
Future uncertainty (FU)	1, 2, 3, 5	3
Visual disorder (VD)	6, 7, 8	3
Motor dysfunction (MD)	10, 15, 19	3
Communication deficit (CD)	11, 12, 13	3
Headaches (H)	4	3
Seizures (S)	9	3
Drowsiness (Dr)	14	3
Hair loss (HL)	16	3
Itchy skin (IS)	17	3
Weakness of legs (WL)	18	3
Bladder control (BC)	20	3

The brain cancer module (QLQ-BN20) is meant for use among brain cancer subjects varying in disease stage and treatment modality (i.e., surgery, chemotherapy, radiotherapy, etc.). It is meant to be complemented by the QLQ-C30. It is composed of 20 items forming 11 symptom scales (7 single item scales and 4 multi-item scales).

All scales and single items are reported on categorical responses, and will be linearly converted to numeric values 0 through 100. Given a scale, the raw score (RS) is computed as the mean of component items over the number of items answered for that scale. Then the scale score (SS) will be computed as following.

For global health status/QoL, and symptom scales/items,

$$SS = \{(RS - 1) / \text{range}\} \times 100.$$

For Functional scales,

$$SS = \{1 - (RS - 1) / \text{range}\} \times 100.$$

If 50% or more of the items are answered for a given scale, the scale score will be computed as described above. If not, the scale score will not be computed. For example, physical functioning contains 5 items (questions 1 through 5), and the scale score is calculated if at least 3 of the items are answered. For single-item measures (dyspnea, insomnia, appetite loss, constipation, diarrhea, and financial difficulties), none of the single-item measures can be computed if not answered. If a scale score cannot be computed, the outcome for that score is left blank.

Global health status/QoL is the primary HRQoL endpoint. The other scales from the QLQ-C30 and QLQ-BN20 will be analyzed on an exploratory basis as secondary HRQoL endpoints. The financial difficulties scale (QLQ-C30) will not be analyzed.

All QoL analyses will be performed for the subset of the ITT population for whom at least one valid post-baseline QoL form has been collected. A subject will not be included in a change from baseline analysis unless a corresponding valid QoL form at baseline has also been collected.

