For each scale, the treatment group differences will be evaluated by analyzing the change from baseline to each of the three post-baseline time-points and to the final measurement (last QoL assessment per subject) using a one-way analysis of variance (ANOVA) model. Simple summary statistics for QoL assessments at each timepoint will also be presented. No adjustment for multiplicity is made since it is exploratory. For QoL assessment data, AbbVie will only perform and present simple summary statistics at each timepoint and change from baseline analysis. Other QoL data will be modeled and analyzed by EORTC.

Changes in HRQoL scores per time point will be evaluated by classifying them according to the 10 point change threshold into 3 categories:

- **Improved:** defined as a 10 point or more improvement (i.e., increase for functional scales and decrease for symptom scales) from baseline.
- **Stable:** defined as a less than 10 point change from baseline.
- **Deteriorated:** defined as a 10 point or more deterioration (i.e., decrease for functional scales and increase for symptom scales) from baseline. Subjects without a valid HRQoL outcome will be considered as having deteriorated.

In case of discrete numbers ($N < 10$), categories may be combined. The subsequent proportions will be compared between treatment arms using a chi-square test in the intent-to-treat population.

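### On the primary quality-of-life scale the 15-point sensitivity threshold sorts every scored patient exactly as the 10-point main analysis does, so it cannot test robustness to the threshold

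*Protocol*

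**What the plan says.** Protocol 10.5 names the main quality-of-life outcome: "The GHQs scale will be used as primary outcome of interest for this study". Each patient's change from baseline is put into one of three categories at a 10-point threshold, and the proportions are compared between arms by chi-square. The Protocol summary likewise makes a change of at least 10 points on this scale the primary HRQoL endpoint. To show that the result is robust, Protocol 10.5 adds that "a clinical relevant threshold of 5 and 15 points will be used", together with a reclassification of patients who have no valid score.

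The scoring is in SAP 10.3 (Quality of Life). The row for the primary scale in Table 4 reads "Global health status/QoL 29, 30 6": two items, item range 6. The table note explains that "Item range is the difference between the possible maximum and the minimum responses to individual items", and "the raw score (RS) is computed as the mean of component items over the number of items answered for that scale". Subtracting 1, dividing by the range and multiplying by 100 gives the 0-100 score. The cut is inclusive: improvement is a "10 point or more improvement (i.e., increase for functional scales and decrease for symptom scales) from baseline".

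The 5- and 15-point analyses appear only in the Protocol. Neither SAP 10.3 nor SAP 10.5 (Sensitivity Analyses) carries them. Neither document mentions the step size of the scale.

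**The concern.** A threshold sensitivity analysis is informative only if some patients can change category when the threshold moves. A scale built from two seven-point items has few possible values, so two different nominal thresholds can fall in the same gap between attainable changes. If 10 and 15 points do so on the primary scale, the stricter of the two planned checks must agree with the main analysis whatever the data are. Reporting that agreement as robustness would present an identity as evidence. A reader would also take a 10-point responder to be someone who changed by about 10 points, when the smallest qualifying change is larger.

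**Working it through.** **The plan's own figure first.** Protocol 10.5 gives 128 patients (64 per arm) for a 10-point difference in means with SD 20, two-sided 5% and 80% power. The normal approximation, 2 × (1.96 + 0.84)² × 20²/10², gives 63 per arm after rounding up; the two-sample t-test gives 63.8, i.e. 64. For 15 points the plan states 28 per arm; the normal approximation gives 28 and the t-test 28.9. Both stated figures reproduce within rounding. They concern a difference between mean changes, which is not tied to the step size of the scale.

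**Step size of the primary scale.** Inputs are from SAP 10.3: 2 items, range 6 (responses 1 to 7), raw score = mean of answered items, score = (raw score − 1)/6 × 100.

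- The mean of two whole numbers moves in steps of 0.5, so the score moves in steps of 0.5/6 × 100 = 100/12 = 8.33. There are 13 possible scores.
- A change is a difference of two such scores: 0, ±8.33, ±16.67, ±25 and so on. None lies from 10 up to 15.
- The smallest change that meets each threshold is 8.33 for 5 points, 16.67 for 10 and 16.67 for 15.

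**Partly answered forms.** The SAP says: "If 50% or more of the items are answered for a given scale, the scale score will be computed as described above". One answered item out of two is therefore enough. Its score moves in steps of 1/6 × 100 = 16.67, which lie on the same grid. Counting forms with one or both items answered, there are 8 × 8 − 1 = 63 response patterns, hence 63 × 63 = 3,969 baseline/follow-up pairs. Enumerating all of them, 0 are classified differently at 10 and 15 points, and 640 differ between 5 and 10.

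**The other scales, complete forms.** Step = 100/(items × range). Financial difficulties is excluded, as planned, which leaves 25 scales in SAP Tables 4 and 5.

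| Scale type | Scales | Step | Smallest change at ≥5 | at ≥10 | at ≥15 |
|---|---|---|---|---|---|
| Global health/QoL (2 items, range 6) | 1 | 8.33 | 8.33 | 16.67 | 16.67 |
| Four items, range 3 | 2 | 8.33 | 8.33 | 16.67 | 16.67 |
| Two items, range 3 | 5 | 16.67 | 16.67 | 16.67 | 16.67 |
| Single item, range 3 | 12 | 33.33 | 33.33 | 33.33 | 33.33 |
| Three items, range 3 | 4 | 11.11 | 11.11 | 11.11 | 22.22 |
| Physical functioning (5 items, range 3) | 1 | 6.67 | 6.67 | 13.33 | 20.00 |

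The 15-point cut differs from the 10-point cut on 4 + 1 = 5 of 25 scales and coincides on 20. On 5 + 12 = 17 scales all three cuts coincide. Partly answered forms loosen this for some longer scales (on a four-item scale, changes of 11.11 and 13.89 become possible), but not for global health/QoL.

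**The case against.** The case for leaving the plan alone is fair. HRQoL is exploratory (Protocol 10.2 and 10.4; SAP 4.6) and outside the testing hierarchy. Protocol 10.5 puts magnitude and relevance ahead of comparative tests. SAP 10.3 also plans an ANOVA of change from baseline on each scale, which uses no threshold. The 5-point check still works on global health/QoL. The 15-point check works on fatigue and communication deficit, the two secondary scales that Protocol 10.5 names as examples. The 10-point rule is applied to each patient exactly as written. Finally, the documents describe 5 and 15 points as clinically relevant and give no support for a higher threshold such as 25.

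All of this stands, and it sets the severity at minor. It does not change the finding: on the scale the Protocol makes primary, one of the two threshold checks cannot disagree with the result it is meant to test. The lack of support for 25 points is a reason to label such a cut plainly, not to keep one that carries no information.

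**Conclusion.** The point holds, at minor severity. On global health/QoL the 10- and 15-point rules are the same rule for every scored patient. It follows from the SAP scoring alone and needs no assumption about the distribution of scores.

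Some stronger readings are tempting but not supported:

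- A reader might infer that every 10-point figure in the plan really means 16.67. That is true only of the patient-level category. The sample-size figure is a difference in means and reproduces.
- A reader might infer that the 15-point results must match the main results in every respect. If the reclassification of missing patients is run together with the 15-point cut, the results can differ, but only through the missing-data rule.
- A reader might put fixed percentages on the effect. Protocol 10.5 gives SD 20 for the scale, not for change from baseline, and patients without a valid outcome count as deteriorated. Percentages from a normal model with change SD 20 would not describe the planned analysis.
- A reader might infer, from the shared formula introduced by "For global health status/QoL, and symptom scales/items", that a fall in global health counts as improvement. Table 4 lists it as a class of its own. The unstated direction is a missing detail that an analyst would fill sensibly, not a reversal.

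**What to change.** Amend Protocol 10.5 and carry the text into SAP 10.3.

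**Global health/QoL only.**
- Keep the 10-point main cut, and report that it requires a change of at least two scale steps (16.67).
- Keep the 5-point cut (one step, 8.33).
- Replace the 15-point cut with three steps (25 points; any threshold above 16.67 and up to 25 has the same effect). Label it a stricter sensitivity cut, not an established clinical threshold.
- State the cuts in steps. A literal threshold of 16.7 would exclude a change of 16.67.

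**Other scales.** Leave 5 and 15 points in place. State that on complete forms the 15-point cut differs from the 10-point cut only for the three-item scales and physical functioning (5 of 25), so agreement on the remaining scales must not be reported as robustness. The new cuts should not be extended to all scales: on physical functioning an 8.33-point cut needs 13.33, the same as the 10-point cut, so a 5-point check that now works would become an identity.

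**Cost.** A short wording change to the Protocol and the SAP, with no new data. The downside is an upper cut with less clinical precedent in the documents than 15 points.

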10.5.1 Missing data

Missing data is a potential major source of bias in HRQoL assessment.

In order to check the potential impact in the study, the compliance mechanism will be investigated prior to initiating the HRQoL analysis. Characteristics of patients with and without valid HRQoL data will be compared and trends over time per dropout pattern will be investigated. Model building will be used in order to investigate whether the compliance mechanism is linked to selected prognostic variables.

Once the main analysis is completed, sensitivity analyses will be undertaken to verify the robustness of the results vis-à-vis the missing data.

In case overall compliance is deemed too low (<50%), only an exploratory analysis will be performed in lieu of the main analysis.

11 Translational research

11.1 General principles for human biological material (HBM) collection

In this study, biological material (tumor tissue) will be shipped from the study site to a designated CRO according to instructions provided in the study specific laboratory manual. Following the tissue analysis for EGFR amplification and EGFRvIII mutation, all biologic material will be centralized and stored at [REDACTED]. From here, the biological material will be used or distributed to the other research laboratories involved in the translational research (TR) projects specified in this protocol or defined in the future.

To allow confirmatory studies for EGFR and other mutations in glioblastoma DNA will be collected as part of the study protocol for confirmatory studies. In addition, the biobank will distribute HBM to the other research laboratories involved in the translational research (TR) projects specified in this protocol or defined in the future.

The following principles apply to storage of HBM:

- The biobank will have a designated manager responsible for collection and will act as a communication point with the EORTC
- The collected HBM should be documented, i.e. the amount remaining and its location.
- The 1410-BTG study steering committee (SSC) will be responsible for TR project review and prioritization, including the consideration of newly proposed TR projects not specified in the protocol. In the absence of a SSC, responsibilities of the SSC are transferred to the Group and/ or EORTC HQ as applicable.

Final decisions on the use of HBM will be determined by a majority vote of the SSC/BTG committee. Additional expertise may be sought through advisory non-SSC/BTG committee members.

Access to HBM (see EORTC Biobanking Policy POL020): HBM may be used for another purpose for which it was originally collected, subject to meeting ethical principles/and is covered by informed consent/ethics approval. In the case of secondary use of HBM, (i.e. for new TR projects that are not specified in the clinical study protocol and that were not foreseen at the time of protocol writing) interested parties may apply for the use of HBM and will follow the next steps:

A short description of the new TR projects will be written and submitted to EORTC HQ for coordination with the SSC/BTG committee.

- The SSC/BTG committee will prioritize the TR projects. Access procedures defined by the SSC/BTG committee will build on the following key points:
 - Project prioritization
 - should be strongly based on scientific merit,
 - should consider the contribution of the different investigators to the trial and TR project,

- will take into consideration if the applicant is an EORTC member or not (whilst maintaining the principle of access to the wider scientific community and commitments owed to study participants and ethical committees).
- Protection of confidentiality must be respected.
- An EORTC HQ feasibility check, including recommendations for regulatory and ethical matters and other restrictions on the use of the HBM, will take place. If in the event the HBM collections are still retained at individual clinical sites, the TR project leader and the involved EORTC Group are responsible for collecting and providing information on availability of HBM for the feasibility assessment.
- Prioritized TR projects will then be reviewed by the Translational Research Advisory Committee (TRAC).

Once SSC/BTG committee prioritization, the EORTC HQ feasibility assessment, and TRAC review are complete and when all applicable competent Ethics Committees approvals are in place and ethical principles are met, the TR project can be activated and HBM release and analysis can commence.

The EORTC Board will mediate any disagreements of opinion between TRAC, the EORTC HQ feasibility assessment, the SSC/BTG committee and the TR project leader(s), as needed.

11.2 Pharmacokinetic Analysis of Blood Samples for ABT-414, Total ABT-806, Unconjugated Cys-mcMMAF, and ADA (nADA)

In this study, pharmacokinetic blood and/or serum samples collected from subjects in Arms 1 and 2 will be shipped from the study site to a designated CRO according to instructions provided in the study specific laboratory manual. Serum or plasma concentrations of ABT-414, Total ABT-806, ADA/nADA, and unconjugated cys-mcMMAF will be determined using validated methods under the supervision of the Drug Analysis Department at AbbVie.

Peak and trough concentrations (C_{max} and C_{trough}) of ABT-414 and total ABT-806 antibody will be summarized from the observed concentration data. A nonlinear mixed effect modeling analysis will be conducted to estimate the population pharmacokinetic parameters of ABT-414, total ABT-806 and cys-mcMMAF such as clearance and volume of distribution. Effect of demographic and/or disease-specific variable(s) on the PK parameters of ABT-414, total ABT-806, and cys-mcMMAF will be examined.

Exposure-response analyses for relevant safety and/or efficacy variables may be conducted to understand the contribution of ABT-414, total ABT-806 antibody, and cys-mcMMAF to efficacy and safety.

11.3 Pharmacodynamic Analysis of Plasma Markers and Serum Markers

Pharmacodynamic plasma and serum samples collected from subjects randomized to Arm 1 and 2 will be shipped from the study site to a designated CRO according to instructions provided in the study specific laboratory manual and will be analyzed by AbbVie. Examination of the plasma and serum components of blood in subjects may reveal patterns of metabolites, cell-free nucleic acids or protein/peptide concentrations that may be further evaluated in future clinical studies to determine any prognostic value and any correlation with clinical response. Serum and plasma samples may be analyzed for predictive or drug-responsive proteomic or nucleic acid markers

11.4 Pharmacogenetic Analysis of Blood Samples - optional

All subjects enrolled in the study may consent to provide samples for the optional pharmacogenetic analysis. These samples will be shipped from the study site to a designated CRO according to instructions provided in the study specific laboratory manual. The PG samples may be analyzed by Abbvie or companies working with AbbVie. DNA samples may be sequenced and data analyzed for genetic factors contributing to the disease or subject's response to ABT-414, or other study treatment, in terms of pharmacokinetics, efficacy, tolerability and safety. Such genetic factors may include genes for drug metabolizing enzymes, drug transport proteins, genes within the target pathway, or other genes believed to be related to drug response or disease. Some genes currently insufficiently characterized or unknown may be understood to be important at the time of analysis. The samples may be analyzed as part of a multi-study assessment of genetic factors involved in the response to ABT-414, drugs of this class, or the disease state. The samples may also be used for the development of diagnostic tests related to the disease or ABT-414 (or drugs of this class). The results of pharmacogenetic analyses may not be reported with the study summary.

